## The Qualitative Interview Study

An individual qualitative interview study will be conducted as part of the overall project.

The aim of the interview study is to explore participants' experiences of the impact of the assigned treatment pathway on their everyday life. From each assigned treatment pathway, 10-12 participants will be interviewed by a research assistant using an interview guide. Participants will be sampled randomly.

Participants will be asked to take part in the interview, when the course of their specific treatment is finalised at week 12, by the clinician overseeing the final rating. If a participant accepts, a follow-up meeting with a research assistant will be scheduled, where the qualitative interview will be conducted.

Both the qualitative interview as well as selection and recruitment of participants will be carried out at end of study week 12, i.e. not when the overall RCT is finalised, to ensure that there will be no interference with the quantitative outcomes of the RCT-study, and to minimise recall bias among participants.

All interviews will be transcribed by a student helper, and the qualitative data will be analysed using reflexive thematic analysis (26).

Figure 1 illustrates the overall study design with the qualitative interview after week 12.

## Statistics and Power Calculation

### Statistics

The difference in HAM-D6 score between baseline and follow up will be compared between the three groups. A F-test will be used to assess if there is a significant difference among the groups. The analysis will be applied to the mITT population using last-observation-carried-forward (LOCF).

The three different treatment groups will be directly compared to each other, i.e. TAU-GP against ALGO, TAU-GP against TAU-P and TAU-P against ALGO. The groups will be compared based on the change in HAM-D6 scores from baseline to endpoint using a two-sided t-test (difference-in-differences [DID] analysis), along with other relevant secondary outcomes.

The DID-analysis will be applied to the mITT population at 12 weeks using LOCF, and the PP12 population.

In secondary analysis, differences between treatment groups regarding changes during the study period for each of the HAM-D6, MDI, PSP, C-SSRS, and Brief INSPIRE-O scores, will be analysed in separate mixed effects models. The models will be analysed with the relevant outcome as dependent variable, and time, treatment, and their interaction as fixed effects as well as patient and centre as random effects, also using the mITT and PP12 populations.

The proportion of responders (defined as a 50% reduction of HAM-D6 score) or remitters (defined as a HAM-D6 score  $\leq 5$ ) will be compared between the three groups, using chi-square tests for association and/or Poisson regression with a robust estimation of the standard error. The same will be applied to the remaining categorical variables. The analyses will be performed by using the mITT population. A similar analysis will be carried out for the categorical variable reasons for treatment discontinuation in the ITT population.

Further, risk of adverse events and serious adverse events is compared by applying Poisson regression with a robust estimation of the standard error in the mITT population.

To investigate the differences in time to all-cause discontinuation and duration of sick leave after baseline between the three groups, compared two and two, the time in the study will be compared by applying a two-sided t-test. Analysis of sick leave days is carried out on the mITT population and time to all-cause discontinuation will be performed on the ITT population.

Concordance between HAM-D6 and MDI will be analysed visually.

Exploratory analyses will extend the primary linear mixed-effects model by adding baseline variables (age, sex, educational level, baseline HAM-D6, duration of untreated depression, age at first episode, psychiatric/physical comorbidity, prior treatment history and DART score). If deemed feasible, non-linear dynamics as the interaction with treatment arm or an estimation using splines will be included. Relevant effects will be reported as regression coefficients or odds ratios with 95 % CIs and visualised in stratified plots where relevant.

All model assumptions are checked visually and sensitivity analyses, using bootstrap to estimate standard errors, are conducted in case of any violations.

All secondary outcomes will be analysed regardless of the significance of the primary outcome.

The statistical analyses will be performed by a statistician at the Department of Psychiatric Research, Aalborg University Hospital, Psychiatry, using Stata 19.

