### Study intervention

In the two treatment as usual arms (TAU-GP and TAU-P), the choice of treatment and the frequency of patient consultations are at the discretion of the general practitioner (GP) and the psychologist. However, the psychologist will utilize cognitive behavioural therapy (CBT) as part of the treatment approach.

In the TAU-GP arm, the GP's can refer patients for psychotherapy, if deemed necessary, after initiation of medication. In the TAU-P arm, the psychologist may request initiation of medication through the general practitioner after psychotherapy, in the form of cognitive behavioural therapy (CBT), has been initiated.

For the algorithm-based treatment arm (ALGO), the GP drafts an individual, algorithm-guided stepped-care plan that merges measurement-based care with pre-set critical decision points (see figure 2). Every 2–4 weeks, validated symptom scores and side-effects are reviewed against evidence-based thresholds. Symptom scale score results are conveyed as “if-then” rules, triggering the next action, e.g. dose optimisation, switch, augmentation, or psychologist referral, as defined at baseline. These structured checkpoints prevent therapeutic drift and ensure the treatment keeps advancing until meaningful improvement is achieved, while still leaving room for clinical judgement and patient preference. The plan is based on the patient’s symptoms, previous treatment history, current clinical guidelines, possible side effects to antidepressants and the general practitioner’s clinical assessment.

The choice of treatment will follow predetermined steps, and the algorithm will include critical decision points (CDPs) at weeks 4, 8 and 12, where treatment efficacy is assessed. This assessment will lead to specific and predetermined adjustments regarding the current treatment (e.g. to continue current treatment or to change choice of treatment from the predefined plan) and in relation to preset “if-then” rules.

[figure not shown]
As a result of lack of tolerability to the current treatment, an earlier switch to an alternative treatment will be possible. In such cases, the algorithm will continue from that point, with a new HAM-D6 measurement conducted four weeks later.

Figure 2 illustrates the baseline measurement of HAM-D6, followed by initial treatment, and subsequent HAM-D6 measurements and treatment decisions at weeks 4 and 8.

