#### Power calculation

To detect a clinically relevant difference of at least 2.25 points of HAM-D6, with a power of 0.80 and a significance level of 0.05 (two-sided), 45 patients are required in each of the three groups (27, 28). To further account for an estimated dropout of 20%, a total of 57 patients are needed in each group.

The standard deviation of the difference in HAM-D6 between baseline and 12 weeks of treatment is assumed to be equal to 3.9 in all three groups (29).

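### The primary F-test and the pairwise t-tests use raw HAM-D6 change without the baseline covariate: valid under randomisation, but precision may be given up that could be had at almost no cost

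*Protocol*

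**What the plan says.** The Statistics section sets the primary comparison: "The difference in HAM-D6 score between baseline and follow up will be compared between the three groups". The test follows: "A F-test will be used to assess if there is a significant difference among the groups". For the three pairs of arms, "The groups will be compared based on the change in HAM-D6 scores from baseline to endpoint using a two-sided t-test". No covariate is named for either test, and a two-sample t-test has no place for one. Under Secondary outcomes, MDI, PSP and Brief INSPIRE-O are also compared pairwise on change from baseline.

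The Power calculation section works on the same scale. The SD of the HAM-D6 change "is assumed to be equal to 3.9 in all three groups", the target difference is 2.25 points, and the result is 45 per arm, or 57 after 20% dropout.

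The Table of Measurements schedules HAM-D6 at week 0. As a covariate it appears once, in an exploratory tier: "Exploratory analyses will extend the primary linear mixed-effects model by adding baseline variables (age, sex, educational level, baseline HAM-D6". The secondary mixed models have "time, treatment, and their interaction as fixed effects as well as patient and centre as random effects", with no separate baseline term.

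**The concern.** Analysing change is the same as subtracting baseline with a slope fixed at 1. The slope that the data support is the correlation times the ratio of follow-up SD to baseline SD, and it need not be 1. Where it differs, the change score carries variance that a fitted slope would remove, and a chance baseline difference between two arms moves their contrast by (1 − slope) per point. These are two views of one source of variance, not two separate costs.

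The Randomisation section names blocks of 3, 6 and 9 and no stratification by severity, so nothing in the design balances baseline HAM-D6. At stake is the precision of the primary test and of the three contrasts that bear on the stated hypothesis, that the algorithm arm does better than both usual-care arms.

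**Working it through.** **Inputs from the protocol.** Difference 2.25; SD of change 3.9; two-sided alpha 0.05; power 0.80; 45 per arm, 57 with dropout; allocation 1:1:1.

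**Assumptions (not in the protocol).** Baseline/week-12 correlation r = 0.3 to 0.7; ratio k of follow-up SD to baseline SD = 1 to 1.6. Arm means (0, 0, 2.25), chosen because they reproduce the stated sample size.

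**1. Reproduce the plan's figure.** Unadjusted one-way F-test, non-central F with df 2 and 3n − 3.
- Sum of squared deviations of the means = 2.25² × 2/3 = 3.375.
- Non-centrality at n = 45: 45 × 3.375 / 3.9² = 9.99. Power is 80.5% (79.6% at n = 44), so 45 is the smallest n that reaches 80%.
- Dropout: 45 / 0.80 = 56.25, rounded up to 57; 3 × 57 = 171.
- At n = 57 the non-centrality is 12.65 and power is 89.4%.
- A pairwise t-test on change at n = 45 has 77% power.

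The stated size is therefore that of an unadjusted change-score F-test, with no credit for baseline adjustment.

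**2. Add the covariate, holding the SD of change at 3.9.**
- Baseline SD: s0 = 3.9 / √(1 + k² − 2rk).
- Slope = rk.
- Residual variance relative to change-score variance = k²(1 − r²) / (1 + k² − 2rk). With k = 1 this is (1 + r)/2.
- Adjusted SD = 3.9 × √(that ratio). F-test power is recomputed with one df fewer.
- Shift of a pairwise change contrast for a one-SE baseline imbalance at 57 per arm = (1 − rk) × s0 × √(2/57).

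The two ends: k = 1, r = 0.3 gives 0.91 / 1.40 = 0.65; k = 1.5, r = 0.7 gives 1.1475 / 1.15 = 0.998.

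| k | r | slope | variance ratio | adjusted SD | F power, 45 | F power, 57 | pairwise power, 45 | one-SE shift, 57 |
|---|---|---|---|---|---|---|---|---|
| unadjusted | – | 1 (fixed) | 1 | 3.90 | 80.5% | 89.4% | 77% | – |
| 1 | 0.3 | 0.30 | 0.65 | 3.14 | 94% | 98% | 92% | 0.43 |
| 1 | 0.5 | 0.50 | 0.75 | 3.38 | 91% | 96% | 88% | 0.37 |
| 1 | 0.7 | 0.70 | 0.85 | 3.60 | 87% | 94% | 84% | 0.28 |
| 1.25 | 0.3 | 0.38 | 0.78 | 3.45 | 89% | 95% | 86% | 0.34 |
| 1.25 | 0.7 | 0.88 | 0.98 | 3.86 | 81% | 90% | 78% | 0.10 |
| 1.5 | 0.3 | 0.45 | 0.87 | 3.64 | 86% | 93% | 83% | 0.26 |
| 1.5 | 0.7 | 1.05 | 1.00 | 3.90 | 81% | 89.5% | 77% | −0.03 |
| 1.6 | 0.3 | 0.48 | 0.90 | 3.69 | 85% | 93% | 82% | 0.24 |
| 1.6 | 0.5 | 0.80 | 0.98 | 3.86 | 81% | 90% | 78% | 0.10 |
| 1.6 | 0.7 | 1.12 | 0.99 | 3.88 | 81% | 90% | 78% | −0.08 |

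**3. Does the secondary mixed model already do this?** No. If week 0 is one of its time levels with a free mean per arm, its week-12 contrast on complete data is the change-score contrast again. It is in any case not the primary test.

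**The case against.** The strongest reply is that nothing here is invalid. Under randomisation the change-score test keeps its type I error and is unbiased on average. Change is the declared comparison, the sample size was worked out on the SD of change, and the F-test meets its 80% as planned. All of that stands.

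A reader might infer that chance imbalance adds a bias on top of the lost power. It does not: it is conditional noise already inside the SD of 3.9.

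A reader might also take the equal-SD figures, 15 to 35% less variance, as what the trial would gain. The documents do not support that. Entry is limited to moderate episodes (Inclusion criteria), and week 12 may mix remitters with non-responders, so a wider follow-up SD is plausible and the gain can then vanish. Nor is the slope certain to be below 1: it reaches 1.05 and 1.12 in two rows above, and the shift changes sign.

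The analysed number also matters. The mITT set keeps anyone with one post-baseline rating, so it may lie between 45 and 57 per arm, and at 57 the unadjusted F-test already has 89.4% power.

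Finally, patients are randomised at screening in an open-label trial and baseline follows within 14 days, so a baseline difference need not be pure chance. That limits any use of this baseline. The change score uses the same value, so the limit does not favour the present plan.

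The exploratory models will yield some baseline-adjusted estimates, but not for the primary test or the planned pairwise t-tests.

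**Conclusion.** The point holds as an efficiency improvement that is close to free, not as an error of validity. The protocol itself fixes unadjusted tests and places baseline HAM-D6 in the exploratory tier, so this is a stated choice and not a detail left to an analysis plan.

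Over the assumed range, adjustment removes between about none and about a third (35%) of the residual variance. Pairwise power at 45 per arm starts at 77% and ends between about 77 and 92%. A one-SE baseline imbalance at 57 per arm moves a change-score contrast by about 0 to 0.4 points, against a target of 2.25. The F-test figures also rest on one arm differing from two equal arms.

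That the tests are unadjusted is certain. How much is lost is not, because the protocol gives neither the correlation nor the separate SDs. In none of the cases examined is the adjusted test worse.

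**What to change.** - Make the primary test the 2-df arm test from a linear model of week-12 HAM-D6 (or its change) on arm plus baseline HAM-D6. Take the three pairwise differences, with 95% confidence intervals, as contrasts from that one model.
- Do the same for MDI, PSP and Brief INSPIRE-O, each with its own baseline.
- If a repeated-measures model is used instead, choose one of two forms: baseline (by visit) as a covariate with only post-baseline visits as outcomes, or week 0 kept as an outcome with a common baseline mean across arms. Using both would put baseline on both sides of the model.
- Correct the exploratory paragraph, which calls the mixed-effects model primary although the Statistics section makes it secondary to the F-test.
- Keep the sample size.

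The cost is a few lines of wording and one residual degree of freedom out of 132 at 45 per arm (3 × 45 − 3). No new data, visits or patients are needed.

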## Aim of the study

The purpose of this study is to investigate the effectiveness of three different treatment pathways for moderate depressive episodes as part of unipolar depressive disorder, through a three-armed, open-label randomised controlled study. Participants will be allocated to one of the three groups in a 1:1:1 ratio.

The three treatment pathways will be as following:

1. Treatment as usual by a general practitioner (TAU-GP).
2. Treatment as usual by a psychologist (TAU-P).
3. An algorithm-based pharmacological treatment by a general practitioner (ALGO).

The primary outcome of the study is to examine whether there is a difference between the three groups. It will be measured by using a F-test from baseline to end of study at 12 weeks, using the Hamilton Depression Scale, 6 item version (HAM-D6).

Additionally, several secondary outcomes will be explored, e.g. the difference in differences (DID) between TAU-GP vs. ALGO, TAU-GP vs. TAU-P and TAU-P vs. ALGO.

The hypothesis is that a tailored algorithm-based treatment regarding patients with depression, treated in general practice, is more effective than treatment as usual (TAU), whether provided by general practitioners (GPs) or psychologists.

Furthermore, a qualitative study will be conducted to investigate the impact of the assigned treatment pathway from the participant's perspectives.

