## Measures and Outcomes

### Modified intention-to-treat (mITT) population and Per Protocol (PP) populations

The modified intention-to-Treat (mITT) population encompasses all randomised participants with at least one post-baseline HAM-D6 rating. The endpoint of the study is 12 weeks.

For participants with premature endpoints, the latest endpoint available will be used with last-observation-carried-forward (LOCF).

The Per Protocol (PP) populations are defined as completers at week 4 (PP4), at week 8 (PP8), or at week 12 (PP12).

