### Secondary outcomes

All secondary outcomes are based on the mITT population unless otherwise specified. The following secondary outcomes will be explored:

- The difference in differences (DID) in HAM-D6 score, from baseline to end of study, between participants in:
  1. TAU-GP and ALGO
  2. TAU-GP-and TAU-P
  3. TAU-P and ALGO
- The DID in C-SSRS score, from baseline to end of study, between participants in:
  1. TAU-GP and ALGO
  2. TAU-GP-and TAU-P
  3. TAU-P and ALGO
- The DID in MDI score, from baseline to end of study, between participants in:
  1. TAU-GP and ALGO
  2. TAU-GP-and TAU-P
  3. TAU-P and ALGO
- The DID in PSP score, from baseline to end of study, between participants in:
  1. TAU-GP and ALGO
  2. TAU-GP-and TAU-P
  3. TAU-P and ALGO
- The impact of the assigned treatment pathway from the participant's point of view and the participant's personal experience of recovery through a self-rating scale (Brief INSPIRE-O). This will also be done using the DID, from baseline to end of study, between participants in:
  1. TAU-GP and ALGO

2. TAU-GP-and TAU-P

3. TAU-P and ALGO

- The concordance between MDI and HAM-D6.
- Duration of sick leave after baseline (indicated in days) within the current depressive episode.
- A Per Protocol analysis at week 12 (PP12) will also be completed for all continuous secondary outcomes.
- A Per Protocol analysis at week 12 (PP12) will also be completed for the primary outcome.
- Between-group difference for adverse events and serious adverse events.
- Between-group difference for the ITT population in reasons for premature discontinuation, time to all-cause discontinuation

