### [Withdrawal and dropout](#)

Withdrawal from the study will occur at the time when any of the discontinuation criterion are fulfilled, as judged by the investigator.

If possible, data regarding all outcome measures will be collected immediately or as soon as possible after the time of withdrawal. The primary outcome measure (HAM-D6) will have the highest priority. The primary reason for discontinuation will be recorded as well as the time of discontinuation. Subjects who have withdrawn will not be replaced.

If a study participant wishes to dropout, an interview regarding the reasons for dropping out will be offered to the patient concerned. The planned next rating session will be executed as soon as possible hereafter.

It is recommended that study participants discuss further treatment with the treating general practitioner responsible for their care.

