## Flowchart of Participant's Course

## Table of Measurements

Week	-2 to -1 Screening	0 Baseline	4	8	12 End of Study	Un-scheduled visit
Meeting form	In person	Virtual meeting	Virtual meeting	Virtual meeting	Virtual meeting	Virtual meeting
Signed Consent Form	X					
Inclusion and exclusion criteria	X					
Oral + written information	X					
Randomisation	X					
Adverse events		X	X	X	X	X
Demographic data	X					
Rating Scales						
HAM-D6		X	X	X	X	X
C-SSRS	X	X	X	X	X	X
PSP		X	X	X	X	
DART		X				
PSE						X*
Self-report forms						
MDI		X	X	X	X	
Brief INSPIRE-O		X	X	X	X	

HAM-D6: The Hamilton Depression Scale, item 6.

C-SSRS: The Columbia-Suicide Severity Rating Scale.

PSE: Present State Examination.

MDI: Major Depression Inventory.

PSP: The Personal and Social Performance Scale.

DART: The Danish Adult Reading Test.

\*In person

All visits and phone calls are scheduled within the defined time frame +/- 3 days. Pre-screening is conducted by a phone call by the investigator or study staff. The written study information will be sent in advance of the screening visit, and if the patient prefers, the letter of consent will also be sent prior to screening. The screening visit is a physical meeting where oral and written information is presented, and written consent can be obtained. Should the patient wish to, they can have at least 24 hours and no more than a week to consider the consent form. A follow-up meeting will be scheduled.

If, during the screening visit, the patient is found to meet all criteria for trial participation, the first treatment visit (baseline visit) will be scheduled within 14 days of the screening. The patient is randomised to treatment at screening.

A virtual baseline meeting is scheduled with the investigator or a competent research assistant. Study visits (virtual meetings) at 4, 8 and 12 weeks, as well as potential telephone calls, are scheduled with the investigator or study staff. Both screening and baseline visits are study related.

Table 1 further visualises the duration of time of each rating scale and interview as well as type of the rating scale, along with the duration of time and type for the different kinds of visits.

	Duration	Type
C-SSRS	1. visit 20 minutes (hereafter 5 minutes)	Rating scale - Interview
PSP	15 minutes	Rating scale - Interview
DART	5 minutes	Rating scale - Interview
HAM-D6	15 minutes	Rating scale - Interview
PSE	60-90 minutes	Semi-structured interview

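### The primary F-test and the pairwise HAM-D6 t-tests carry early ratings forward to week 12, which biases them if dropout is unequal; the text also calls two different analyses primary

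*Protocol*

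**What the plan says.** *Aim of the study* names the primary test: "It will be measured by using a F-test from baseline to end of study at 12 weeks". *Statistics* repeats the F-test and adds: "The analysis will be applied to the mITT population using last-observation-carried-forward (LOCF". The pairwise t-tests on HAM-D6 change in the same section also use LOCF in mITT, and are repeated in PP12.

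The population section states the rule again: "For participants with premature endpoints, the latest endpoint available will be used with last-observation-carried-forward (LOCF". It defines mITT as a set that "encompasses all randomised participants with at least one post-baseline HAM-D6 rating". One early rating is therefore enough to enter the primary analysis, and a patient with none leaves it.

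Under *Withdrawal and dropout*, outcome data are to be collected, if possible, at or soon after withdrawal, and "The primary outcome measure (HAM-D6) will have the highest priority". Continued rating to week 12 after withdrawal is not stated.

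Three other elements bear on the point:
- A mixed model for HAM-D6 is planned as a secondary analysis, with "time, treatment, and their interaction as fixed effects as well as patient and centre as random effects".
- *Secondary outcomes* adds a completers analysis: "A Per Protocol analysis at week 12 (PP12) will also be completed for the primary outcome". It also plans between-arm comparisons of discontinuation.
- The exploratory paragraph of *Statistics* speaks of extending the primary mixed-effects model, although the F-test is primary everywhere else.

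**The concern.** LOCF assumes that nothing changes after the last rating. Here change is expected: the ALGO arm has decision points at weeks 4 and 8 that exist to produce further improvement. A patient who leaves at week 4 is scored as if improvement had stopped there. If one arm loses more patients, or loses them earlier, its mean week-12 improvement is understated relative to the others. Part of the observed difference then reflects when patients left rather than what treatment did.

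The protocol expects 20% dropout and gives no arm-specific rate. Unequal dropout is plausible, because the trial is open-label, the pathways differ, and inability to follow the assigned arm's treatment is a discontinuation criterion. Either direction is possible, so LOCF cannot be defended as conservative.

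The pairwise HAM-D6 contrasts matter as much as the F-test. They address the hypothesis that ALGO is better than either form of usual care, and they carry the same rule.

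The two uses of the word primary are a separate defect that needs no assumption. As written, a reader could not say which analysis decides the trial if the F-test and the mixed model disagreed.

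**Working it through.** **1. The plan's own figure.** Inputs from *Power calculation*: difference 2.25, SD of change 3.9, alpha 0.05, power 0.80. For a three-group F-test with means 0, 0, 2.25, the noncentrality is n × Σ(mean − grand mean)² / 3.9². Power is 0.796 at n = 44 and 0.805 at n = 45. Allowing for dropout, 45/0.8 = 56.25, so 57 per arm and 171 in all. The stated figures reproduce. With 57 fully observed patients per arm, power is 0.894.

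**2. Size of the LOCF shift.** Within an arm, shift = dropout rate × total improvement × share of improvement not yet reached at the last rating. The following are assumptions, not protocol figures: improvement of 5–9 points; 40–50% of it by week 4 and 75–80% by week 8; dropouts split evenly between weeks 4–8 and 8–12; every dropout rated at least once after baseline; no true week-12 difference.

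Share missed, without a withdrawal rating:
- fast course: mean(0.50, 0.20) = 0.35
- slow course: mean(0.60, 0.25) = 0.425

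Share missed, with a withdrawal rating midway between visits:
- fast course: mean(0.35, 0.10) = 0.225
- slow course: mean(0.425, 0.125) = 0.275

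Largest false gap between arms at 10/20/30% dropout:
- with the rating: 0.2 × 5 × 0.225 = 0.225 to 0.2 × 9 × 0.275 = 0.495 points
- without it: 0.2 × 5 × 0.35 = 0.35 to 0.2 × 9 × 0.425 = 0.765 points

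**3. Null rejection rate** (noncentral F, 2 df, 57 per arm, SD 3.9):

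| Dropout by arm | With withdrawal rating | Without |
|---|---|---|
| 20/20/20% | 5.0% | 5.0% |
| 15/20/25% | 5.2–5.9% | 5.4–7.1% |
| 10/20/30% | 5.7–8.6% | 6.7–14.0% |

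Simulation of the LOCF F-test agrees to within a few tenths of a point in most cases. It used assumed SDs of 2.5, 3.2, 3.6 and 3.84 at weeks 0, 4, 8 and 12, and correlations of 0.3–0.7. At 10/20/30% it gives about 6% and 8.8% with the rating, and about 6.6–6.9% and 13% without. At 15/20/25% with the rating it goes as low as 5.1%. If one third of dropouts have no post-baseline rating and leave mITT, the 10/20/30% formula values fall to 5.4–6.9% and 5.9–9.7%.

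**4. Equal 20% dropout, true effect 2.25, benefit accruing linearly.** Dropouts carry on average two thirds of the effect with a withdrawal rating and half without.
- With: 2.25 × (0.8 + 0.2 × 2/3) = 2.10, power 0.847.
- Without: 2.25 × (0.8 + 0.2 × 0.5) = 2.025, power 0.818. Simulation gives 74–82% here.

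**5. The alternative.** At 10/20/30% without a withdrawal rating, a repeated-measures model with unstructured covariance and baseline by visit rejected in 5.3% and 4.6% of 3,000 null trials each, with bias of about 0.02 points or less. At equal 20% dropout its power was 83–89% across two sets of assumptions. A model with only a patient random effect rejected in 12–13% under the null at unequal dropout. That result depends on the assumed growth in SD from 2.5 to 3.84. The mixed models were not simulated with off-schedule withdrawal ratings.

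**The case against.** The strongest reply is about size. The protocol gives HAM-D6 priority at withdrawal. With that rating, moderate imbalance leaves the error rate almost untouched, and visible inflation needs something like a threefold difference in dropout. This stands. A reader might infer from the 14% figure that the planned test badly fails its error rate. The documents do not support that, because 14% needs 10/20/30% dropout, a large and slow improvement, and no withdrawal ratings. Since the rating is only to be taken if possible, the truth may lie between the two columns.

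A reader might also infer that the trial is underpowered because of LOCF. Under equal dropout, power stays near the stated 80%, because inflating to 57 leaves room. What is lost is that margin, and the estimate shrinks to about 2.0–2.1 points.

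It can also be said that the secondary mixed model, the completers analysis and the discontinuation comparisons may expose the problem. They may, but none alters the primary conclusion, and completers are a selected group. The one sensitivity analysis that *Statistics* names, bootstrap standard errors, does not address missing data.

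Finally, covariance structure and imputation detail are often left to an SAP, and none is at hand. That is fair for the details. It does not cover the LOCF rule or the conflicting primary label, both of which the protocol states. Nor is the unadjusted change score an error: it is a valid analysis and not part of this point.

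**Conclusion.** The point holds and should be fixed before any outcome data are examined. The protocol fixes LOCF for the primary F-test and for the pairwise HAM-D6 t-tests. That biases the week-12 comparison if dropout is unequal while patients improve, and dilutes a true effect even if it is equal.

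Confidence is high in the mechanism and limited in the size. Under the stated assumptions the null rejection rate is about 5.1–5.9% (15/20/25%) or 5.7–8.8% (10/20/30%) with withdrawal ratings, and about 5.4–7.1% or 6.6–14% without. Trajectory, dropout by arm and its timing, and visit correlations are all assumed, so these are illustrations and not bounds. The documents do not show that dropout will be unequal, or which arm would gain.

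The contradiction over which analysis is primary holds without any assumption.

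**What to change.** 1. Make the primary analysis a repeated-measures mixed model of HAM-D6 at weeks 4, 8 and 12. Use categorical visit by arm, baseline HAM-D6 by visit, centre as already planned, and a within-patient covariance that does not force equal variances and correlations. The primary test is the 2-df arm difference at week 12. The secondary model should not be promoted without settling that covariance.
2. Take the three pairwise HAM-D6 contrasts at week 12 from the same model, so that they and the overall test treat missing data alike.
3. State how off-schedule withdrawal ratings are assigned to a visit.
4. Keep the LOCF F-test as a sensitivity analysis. Add one for departures from missing at random that includes patients without a post-baseline rating, for example multiple imputation with imputed week-12 scores shifted by 1, 2 and 3 points, arm by arm.
5. Edit *Aim of the study*, the mITT section and both parts of *Statistics* so that only one analysis is called primary.

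The cost is text: 171 patients and the visit schedule stay as they are. The downside is that the primary result then relies on missing at random, which cannot be tested. If unseen week-12 scores of dropouts are 1–3 points worse than predicted, a dropout gap of 0.2 between arms gives a bias of 0.2 × 1 to 0.2 × 3, or 0.2–0.6 points; hence the added sensitivity analysis. One weakness remains under either method. According to *Table of Measurements*, "The patient is randomised to treatment at screening", and baseline HAM-D6 is rated at the later baseline visit, after open-label allocation. The change score shares this.
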